6 DISCONTINUATION

6.1 Discontinuation of Individual Subject(s) From Study Treatment

A discontinuation from treatment is a subject who enrolled in the study and for whom study treatment is permanently discontinued for any reason. The reason for discontinuation from study treatment must be documented in the subject's medical records.

A subject must discontinue study treatment for any of the following reasons:

- Subject requests to stop treatment.
- Any clinical AE, laboratory abnormality or intercurrent illness, in the opinion of the investigator, indicates continued treatment is not in the best interest of the subject.
- Parent(s) or legal guardian withdraws consent.
- Subject experiences a systemic infusion-related reaction (IRR) such as hypotension, dyspnea, chills, dizziness, paresthesia and hypoesthesia attributable to study drug during or shortly after the intravenous administration; however, in case of an infusion-related reaction, the infusion must be stopped immediately and the subject must be discontinued from treatment.

Note: If the IRR signs and symptoms are mild and self-limiting, the subject may continue in the study at the discretion of the investigator.

- Serious hypersensitivity or severe skin reactions, such as anaphylaxis or Stevens Johnson syndrome, have been reported during treatment with other azoles. If subject develops a severe hypersensitivity adverse reaction without alternative etiology, the subject must be discontinued from treatment.
- Investigator's decision that further treatment is not in the best interest of the subject.
- Female subject becomes pregnant.
- Subject is lost to follow-up despite diligent efforts to contact.

Discontinuation of the subject from treatment should be considered if a subject experiences an increase in liver enzymes. For specific liver abnormalities, refer to [Appendix 12.5].

All subjects who discontinue study treatment will remain in the study and should continue to be followed for protocol specific follow-up procedures as outlined in [Table 1 Schedule of Assessments]. The only exception to this is when the subject specifically withdraws consent for any further contact, with him/her or persons previously authorized by the participant to provide this information.

6.1.1 Lost to Follow-up

Every reasonable effort is to be made to contact any subject lost to follow-up during the course of the study to complete study-related assessments and record outstanding data.

6.2 Discontinuation of the Site

If an investigator intends to discontinue participation in the study, the investigator must immediately inform the sponsor.

6.3 Discontinuation of the Study

The sponsor may terminate this study prematurely, either in its entirety or at any study site, for reasonable cause provided that written notice is submitted in advance of the intended termination. Advance notice is not required if the study is stopped due to safety concerns. If the sponsor terminates the study for safety reasons, the sponsor will immediately notify the investigator and subsequently provide written instructions for study termination.

7 STATISTICAL METHODOLOGY

A statistical analysis plan (SAP) will be written to provide details of the analysis, along with specifications for tables, listings and figures to be produced. The SAP will be finalized before the database soft lock at the latest. Any changes from the analyses planned in SAP will be justified in the clinical study report.

In general, continuous data will be summarized with descriptive statistics (number of subjects, mean, standard deviation, minimum, median and maximum) and frequency and percentage for categorical data.

7.1 Sample Size

A sample size of approximately 30 subjects is planned. No formal sample size calculation was performed.

Evaluable subjects are subjects who have received at least 1 dose of study drug. Every effort will be made to achieve at least 5 evaluable subjects per age cohort: 1 to < 12 years of age and 12 to < 18 years of age. The sponsor reserves the right to stop enrollment if the cohort requirements are not achieved. There will be no replacements for any subject that is enrolled, but later determined to be non-eligible.

7.2 Analysis Sets

Detailed criteria for analysis sets will be laid out in classification specifications and the allocation of subjects to analysis sets will be determined prior to database hard-lock.

7.2.1 Full Analysis Set (FAS)

The full analysis set (FAS) will consist of all subjects who are enrolled and receive at least one dose of study drug. This will be the primary analysis set for efficacy analyses.

7.2.2 Modified Full Analysis Set (mFAS)

The modified FAS (mFAS) will consist of the subset of the FAS subjects who have either probable or proven IA or IM diagnosis at baseline or up to 10 days after first dose. The mFAS will be a secondary analysis set for efficacy analyses. Select demographic and baseline characteristics may also be summarized for the mFAS.

7.2.3 Safety Analysis Set (SAF)

The safety analysis set (SAF) will consist of all subjects who are enrolled and receive at least 1 dose of study drug and will be used for safety analyses. For this study, the SAF is the same as the FAS. For the statistical summary of the safety data, the SAF will be used.

7.2.4 Pharmacokinetic Analysis Set (PKAS)

The pharmacokinetic analysis set (PKAS) consists of all subjects who took at least 1 dose of study drug and who have at least 1 plasma concentration. Inclusion of subjects in the PKAS with missing data or major protocol deviations will be considered by the pharmacokineticist on a case-by-case basis.

The PKAS will be used for all summaries and analyses of the pharmacokinetic data.

7.3 Demographics and Baseline Characteristics

Demographics and baseline characteristics (age, sex, race, ethnicity, weight, height and body mass index) will be summarized for each analysis set.

7.3.1 Subject Disposition

The number and percentage of subjects who completed and discontinued treatment and reasons for treatment discontinuation will be presented for all enrolled subjects and for subjects in the SAF by age cohort and overall. Similar tables for screening disposition, investigational period disposition and follow-up disposition will also be presented for all enrolled subjects by age cohort and overall. All disposition details and dates of first and last evaluations for each subject will be listed.

7.3.2 Previous and Concomitant Medications

All previous and concomitant medications will be summarized for subjects in FAS and SAF analysis sets and will also be presented in listings.

7.3.3 Medical History

Medical history for each subject will be presented in a listing.

7.4 Analysis of Efficacy

This is an open-label trial without a comparator group, and its analysis will be descriptive. No formal inferential analyses will be performed. Appropriate confidence intervals (CI) will be part of the description/summary of the data. Efficacy variables will be summarized with frequencies and percentages for the FAS and mFAS sets unless otherwise specified. For each efficacy endpoint, a summary will be presented for overall subjects and by subjects in each age cohort.

7.4.1 Analysis of Primary Efficacy Endpoint

7.4.1.1 Primary Efficacy Analysis

The primary efficacy endpoint of crude rate in all-cause mortality through day 42 will be analyzed on FAS population as a primary analysis. Any death that occurred after first dose of study drug through day 42 will be included.

Each subject will be classified as either a death or alive. Subjects who died on or before day 42, as well as subjects who are lost to follow-up before day 42 will be counted as deaths. The crude all-cause mortality rate will be calculated by dividing the number of deaths by the number of FAS subjects, and a 2-sided exact 95% CI will be calculated.

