7.4.2 Analysis of Secondary Efficacy Endpoints

7.4.2.1 Analysis of Key Secondary Endpoints

Crude rate in all-cause mortality through day 84/EOT is considered as key secondary efficacy endpoint, which will be analyzed as described in [Section 7.4.1 Primary Analysis] for FAS and mFAS analysis sets. Any death that occurred after first dose of study drug through day 84/EOT will be included.

Subjects who die on or before day 84/EOT, as well as subjects who are lost to follow-up before day 84/EOT, will be counted as deaths.

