5.2 Efficacy Endpoints

5.2.1 Primary Efficacy Endpoint

The primary efficacy endpoint will be all-cause mortality through day 42. Any death that occurred after first dose of study through day 42 will be included. Any lost to follow-up between first dose and day 42 will be considered a death.

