6.4.1.1 Analysis for Primary Efficacy Endpoint(s)

The primary efficacy endpoint will be all-cause mortality through day 42. Any death that occurred after first dose of study drug through day 42 will be included where each subject will be either classified as a dead or alive. Subjects who died on or before day 42, as well as subjects who are lost to follow-up before day 42 will be counted as deaths. The crude all-cause mortality rate will be calculated by dividing the number of deaths by the number of FAS subjects, and a 2-sided exact 95% CI will be calculated.

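### The mortality rule does not say how to classify a subject who withdraws consent for all contact before day 42 (or day 84) with vital status unknown; read literally, that subject counts as alive

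*Protocol*

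**What the plan says.** Protocol 7.4.1.1 sets the endpoint and population: "The primary efficacy endpoint of crude rate in all-cause mortality through day 42 will be analyzed on FAS population as a primary analysis". The classification has two classes: "Each subject will be classified as either a death or alive". Subjects who died by day 42, "as well as subjects who are lost to follow-up before day 42 will be counted as deaths". The denominator is the number of FAS subjects, with a two-sided exact 95% CI.

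The SAP repeats this. In 5.2.1: "Any lost to follow-up between first dose and day 42 will be considered a death". In 6.4.1.1: "each subject will be either classified as a dead or alive".

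The key secondary endpoint follows the same rule. Protocol 7.4.2.1 covers those who die by the later time point, "as well as subjects who are lost to follow-up before day 84/EOT, will be counted as deaths", and SAP 5.2.2.1 agrees. The efficacy paragraph of the Synopsis states the rule for all three time points. SAP 6.4.2 gives the day 84 and EOT calculation but has no sentence on subjects of unknown status.

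Protocol 6.1, on stopping treatment, lists "Parent(s) or legal guardian withdraws consent" as one reason and loss to follow-up after failed attempts at contact as another. It keeps subjects who stop treatment in follow-up, with one exception: "The only exception to this is when the subject specifically withdraws consent for any further contact" (with the subject or with persons authorised earlier to give information).

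None of the mortality sections mentions withdrawal of consent, or unknown vital status from any cause other than loss to follow-up.

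**The concern.** The protocol foresees a subject who may not be contacted at all. If that happens before day 42, vital status may be unknown, yet the endpoint needs an answer: the classification has no third class, and the FAS denominator does not let the subject drop out. The only routes to a death are dying and being lost to follow-up. A family that forbids contact does not fit the description of failed contact in Protocol 6.1, so on the plain wording the subject lands in alive.

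Two children with the same missing information could therefore be an event and a non-event. In an open-label study of about 30 subjects, a point that affects the primary rate should not be left for someone to settle after the data have been seen.

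**Working it through.** **No figure in the plan to reproduce.** The study is descriptive, and the planned 30 subjects rest on no formal calculation. What can be checked is how far the estimate moves with the classification.

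**Inputs**
- N = 30, the approximate planned size (Protocol 7.1). N = 25 is also used, the evaluable minimum in Protocol 2.2.1.
- d = deaths by day 42, including losses to follow-up counted as deaths. Not in the documents; assumed 3, 5 or 9.
- w = subjects with consent to all contact withdrawn before day 42 and vital status unknown. Not in the documents; assumed 0 to 3.
- k = how many of those w had in fact died by day 42, from 0 to w.

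**Formulas**
- Literal reading: rate = d/N.
- Same treatment as loss to follow-up: rate = (d + w)/N.
- Difference between the two codings: w/N.
- Understatement under the literal reading attributable to these subjects: k/N, so at most w/N and zero if all survived.
- Exact 95% CI (Clopper-Pearson) for x events: lower limit = 2.5% quantile of Beta(x, N − x + 1); upper limit = 97.5% quantile of Beta(x + 1, N − x).

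**Per subject:** 1/30 = 3.3 percentage points; 1/25 = 4.0 points.

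**Range at N = 30**

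| d | w | Counted as alive | Counted as deaths |
|---|---|---|---|
| 3 | 1 | 10.0% (2.1–26.5) | 13.3% (3.8–30.7) |
| 3 | 2 | 10.0% (2.1–26.5) | 16.7% (5.6–34.7) |
| 3 | 3 | 10.0% (2.1–26.5) | 20.0% (7.7–38.6) |
| 5 | 2 | 16.7% (5.6–34.7) | 23.3% (9.9–42.3) |
| 5 | 3 | 16.7% (5.6–34.7) | 26.7% (12.3–45.9) |
| 9 | 2 | 30.0% (14.7–49.4) | 36.7% (19.9–56.1) |
| 9 | 3 | 30.0% (14.7–49.4) | 40.0% (22.7–59.4) |

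Over w = 0 to 3 the two codings differ by 0 to 10.0 points (3/30).

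**Subgroups.** Efficacy is also reported by age cohort, where the aim is at least 5 evaluable subjects each, and by type of infection. In a group of 5, one such subject moves the rate by 1/5 = 20 points.

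**Direction.** Let s be the number of subjects lost to follow-up who in fact survived. The net error of the literal rule is (s − k)/N. It can have either sign.

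**The case against.** The case for leaving the text alone has several parts.

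*Alive is an inference.* This is correct. No section says that a withdrawn subject is alive, and loss to follow-up is not defined for the endpoint. An analyst could apply SAP 5.2.1 to anyone not followed to day 42, which would make the same subject a death. The two bullets in Protocol 6.1 are reasons for stopping treatment, not endpoint definitions. But two defensible codings of one subject on the primary endpoint is itself a reason to write the rule down.

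*The no-imputation principle* (Protocol 7.9, SAP 6.9.1) does not settle it. Coding unknown status as alive is also an imputation, and counting losses to follow-up as deaths is already an exception not listed there.

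*The gap is narrow.* This is also correct. Stopping treatment does not open it, because follow-up continues. Only refusal of all contact, before the time point and with status unknown, does so. It matters little at EOT, which the protocol defines as the date of the last dose, when status is ordinarily known.

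*There is mitigation.* SAP 6.4.1.2 gives a Kaplan-Meier estimate that censors subjects without a reported death at their last assessment, so a withdrawn subject is not carried forward as a day 42 survivor. Reasons for discontinuation are tabulated and subjects are listed. This helps, but the Kaplan-Meier analysis also censors losses to follow-up, a different convention that leaves the crude primary rate unresolved.

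A reader might go further and infer that mortality is understated, that withdrawals follow clinical deterioration, or that the site's disposition code decides the event. The documents support none of these. Understatement needs a withdrawn subject who died by the time point. No withdrawal rate or link to deterioration is given. Mortality status is a scheduled assessment of its own (Table 1), and nothing derives it from the disposition code.

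**Conclusion.** The point holds as a gap in the rule for the primary and key secondary endpoints. Taken literally, the two-way classification over the full FAS defaults a fully withdrawn subject of unknown status to alive, while an uncontactable subject of equally unknown status is a death. This could understate mortality by up to 3.3 percentage points per such subject at n = 30. The full amount applies only if that subject died by the time point; if the subject survived, there is no understatement.

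How many such subjects there will be is an assumption; with none, the gap has no effect. The documents do not establish that mortality will be understated overall, because counting surviving losses to follow-up as deaths pushes the other way.

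**What to change.** Base the rule on whether vital status is known. In the Synopsis (efficacy paragraph), Protocol 7.4.1.1 and 7.4.2.1, and SAP 5.2.1, 5.2.2.1 and 6.4.1.1, replace the loss-to-follow-up condition with: *whose vital status at day 42 (84/EOT) is unknown for any reason, including withdrawal of consent*. Add the same rule to SAP 6.4.2 as a new sentence, since there is no phrase there to replace. In the mortality tables, show observed deaths and deaths assumed for unknown status on separate rows.

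This extends the sponsor's own worst-case convention. It costs a phrase in six places, one added sentence and one table row, with no new data or procedures. The drawback is that reported mortality may be slightly less favourable, and is overstated if withdrawn subjects survived: by (w − k)/N, again 3.3 points each at n = 30. The separate rows make that visible.

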7.4.1.2 Secondary Efficacy Analysis

The same analysis of the primary endpoint as described in [Section 7.4.1 Primary Analysis] will be conducted using the mFAS.

7.4.2 Analysis of Secondary Efficacy Endpoints

7.4.2.1 Analysis of Key Secondary Endpoints

Crude rate in all-cause mortality through day 84/EOT is considered as key secondary efficacy endpoint, which will be analyzed as described in [Section 7.4.1 Primary Analysis] for FAS and mFAS analysis sets. Any death that occurred after first dose of study drug through day 84/EOT will be included.

Subjects who die on or before day 84/EOT, as well as subjects who are lost to follow-up before day 84/EOT, will be counted as deaths.

7.4.2.2 Analysis of Additional Secondary Endpoints

Additional secondary efficacy endpoints include the overall, clinical, radiological and mycological response through day 42, day 84 and EOT. An Adjudication Committee (AC) will be utilized to confirm the diagnosis and overall, clinical, radiological and mycological response of IA or IM at each time point.

Crude success rates and 2-sided exact 95% CIs will be calculated and summarized for FAS and mFAS analysis sets.

7.5 Analysis of Safety

7.5.1 Adverse Events

AEs will be coded using MedDRA.

TEAE is defined as an AE observed after starting administration of the study drug through 30 days after the last dose. The number and percentage of subjects with treatment-emergent AEs, SAEs, AEs leading to withdrawal of treatment and AEs related to study drug will be summarized by MedDRA system organ class, MedDRA preferred term for overall subjects and by subjects in each cohort. The number and percentage of AEs by severity will also be summarized. All AEs will be listed.

A study drug-related TEAE is defined as any TEAE with a causal relationship of YES by the investigator.

7.5.2 Laboratory Assessments

For quantitative laboratory measurements descriptive statistics will be used to summarize results and change from baseline for subjects in the SAF by treatment visit.

Shifts relative to normal ranges from baseline to each time point during treatment period in lab tests will also be tabulated. Laboratory data will be displayed in listings.

